6.3 Adjustment for Covariates

Not applicable

6.4 Handling of Dropouts, Missing Data, and Data Discrepancies

Unless specified otherwise, in deriving the total (sum) score, the total score will be derived from all available item scores and scaled accordingly. For example, the total score of 7 items will be calculated as 7x (times) average of all available items score out of the 7 intended scores. In case the analysis week is extended to be >7 calendar days, the total score for the week will be calculated as 7 x average of all available daily scores for the analysis week. Also, scores will be set to missing when no scores are recorded for a given 7 day period. AEs with incomplete information for start or stop dates (i.e., either day or month is missing) will be considered treatment-emergent (TEAE) unless the partial start date or the stop date confirms the AE started or ended prior to Study Day 1 (e.g., the day of the AE start date is unknown but the month and year indicate that the AE starts prior to Study Day 1). AEs with missing relationship to study drug will be included in the “Related” category for the summary tables. AEs with missing severity will not be included in the summary table but will be footnoted.

When there is incomplete information regarding dosing dates for prior and concomitant medication, the medication will be considered as a concomitant medication unless it contradicts with the stop date. For example, a medication will be considered a prior medication if the month and year of the end date indicates a date before Study Day 1 even though the start date could be missing.

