Concomitant Medications	Second-generation H1-antihistamines as concomitant medication once daily and up to 4 times daily on demand (drug intake to be documented in the patient diary).
Safety Evaluations	
Safety and tolerability will be assessed throughout the study by monitoring and evaluating adverse events (AEs), including any complications resulting from the IV infusion. All treatment-emergent adverse events (TEAEs) will be collected from the start of study drug administration through 8 weeks after last dose received or Early Termination (ET). Severity will be assessed using the National Cancer Institute (NCI) Common Terminology Criteria for Adverse Events (CTCAE) Version 4.03. All AEs will be assigned a severity grade and relationship to study drug.
 
Additional safety evaluations include clinical laboratory tests, including anti-drug antibody to AK002, complete blood counts, chemistries, and urinalyses, ECGs; and vital signs.

Statistical Methodology	All subjects who received a dose of study drug will be included in the analysis. All safety data will be listed. Where appropriate, summary statistics will be provided (number of non-missing values, mean, median, standard deviation, minimum, and maximum for continuous variables, and number and percentage for categorical variables) for all measures, including demographic and baseline values, clinical scores and safety endpoints.
Rationale for Amendment 4.1	
The following modifications have been incorporated into Amendment 4.1 of the protocol.
 
 
• Procedures that allow subjects in the CholU, UF, and CSU-XOLAIR® (omalizumab) failure cohorts who received all 6 infusions of AK002, were followed through Day 155, and demonstrated severe symptoms of urticaria following discontinuation of treatment, to be offered the option to receive extended dosing with up to 12 additional doses of AK002. Offering extended dosing allows subjects with no other treatment options continued access to AK002 and the benefit obtained during the initial 6 infusions. It also allows for collection of longer-term efficacy, safety, and tolerability data of AK002.
 
• PK will be analyzed retroactively using backup blood samples.
 

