6.1 General Methodology

All statistical analyses will be conducted using SAS Version 9.4 or later on the Microsoft® Windows Operating System.

Continuous data will be summarized using n (number of subjects with non-missing observations), mean, median, standard deviation (SD), minimum value, and maximum value. Categorical data will be summarized using the frequency count and percentage (n, %) of subjects in each category. Number of subjects with non-missing values and number of subjects with missing values (e.g., Not Done) will be presented, where appropriate. Subjects with missing values will not contribute to the denominator of percentage calculations. Counts of zero in any category will be presented without percentage.

All endpoints will be summarized by the individual applicable cohorts (CholU, UF, CSU-XN or CSU-XF). Where appropriate, the summaries will also be carried out for all 4 cohorts combined.

Two-sided 95% confidence interval (CI) may be presented for the mean or percentage.

The precision rules for the presentation of summary statistics will be:

- Sample size (n, N) and number of missing responses (if displayed) – Integer
- Mean, CI – One more decimal place than reported/collected
- Standard deviation – Two more decimal places than reported/collected
- Median, other percentile, minimum, maximum – Same number of decimal places as reported/collected
- Ratio – two decimal places
- Percentage – one decimal place generally, or two decimal places for <0.1%

The data summaries will be accompanied by individual subject data listings. All data available from diary, questionnaires, eCRF, and external transfer (e.g., labs) will be listed and will include relevant and pertinent subject information, e.g. study day. The listings will be sorted in the order of Cohort and unique subject ID, and assessment name and assessment date/time.

Dates will be presented in the ISO-8601 format YYYY-MM-DD. Times will be displayed in 24-hour clock format. Numbering for tables, figures and listings will follow ICH E3 Guidelines ([ICH, 1996](#)).

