7.10 Safety Analyses

7.10.1 Adverse Events

Safety assessments will be based mainly on the nature, frequency, relationship, and severity of adverse events (AEs). AEs will be coded by primary system organ class (SOC) and preferred term (PT) according to the Medical Dictionary for Regulatory Activities (MedDRA) version 21.0. The treatment-emergent adverse events (TEAEs) will be summarized by the number and percentage (n and %) of subjects in each SOC and PT. For summaries by relationship to study drug, “possibly related” will be combined with “related”, and “unlikely/remote related” will be combined with “not related.” When multiple AEs are reported with the same preferred term, the AE of the strongest relation will be included in the summary by relationship, and the AE of the most severe grade will be included in the summary by severity table.

The following AE incidence tables will be presented.

- Overview of TEAEs to include
 - Number (%) of subjects who reported at least one TEAE
 - Number (%) of subjects who reported at least one treatment-related TEAE
 - Number (%) of subjects who reported at least one severe TEAE
 - Number (%) of subjects who reported at least one serious TEAE
 - Number (%) of subjects who reported at least one TEAE leading to treatment discontinuation
- TEAEs by PT sorted by decreasing order of subject incidence in the combined cohort
- TEAEs by SOC and PT sorted alphabetically
- Study Drug-Related TEAEs by SOC and PT
- TEAEs Grade 2+ Severity by SOC and PT

- TESAEs by SOC and PT
- TEAEs leading to study drug discontinuation by SOC and PT

Select TEAEs of pain, tenderness, erythema/redness, induration/swelling, nausea/vomiting, diarrhea, headache, fatigue, and myalgia will be summarized with n and % by toxicity grade.

All AEs will be listed with onset/stop day, relationship to study drug, severity, action taken, and outcome. Pertinent subject information including cohort and demographics will also be included. Separate listings will be provided for TEAEs leading to study discontinuation and Treatment-emergent serious AEs (TESAEs).

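### Adverse events with no severity grade are left out of an unnamed summary table, so counts of subjects with Grade 2+ or severe events can be too low and never too high

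*SAP*

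**What the plan says.** SAP 6.4 has a separate rule for each kind of gap in an adverse event record.

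- **Severity:** "AEs with missing severity will not be included in the summary table but will be footnoted". The table is singular and is not named.
- **Relationship:** "AEs with missing relationship to study drug will be included in the" Related category.
- **Dates:** an event with a partial date is treated as treatment-emergent unless the known part of the date shows otherwise.

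SAP 7.10.1 plans several outputs that need a grade. The overview has a line for the "Number (%) of subjects who reported at least one severe TEAE". There is a table of "TEAEs Grade 2+ Severity by SOC and PT". Selected events are also tabulated by toxicity grade. When a preferred term recurs in a subject, "the AE of the most severe grade will be included in the summary by severity table".

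Three other passages bear on the point. SAP 6.1 sets a general rule: "Subjects with missing values will not contribute to the denominator of percentage calculations". SAP 7.10.1 names no denominator for the adverse event tables. The listing is complete: "All AEs will be listed with onset/stop day, relationship to study drug, severity, action taken, and outcome". The protocol synopsis expects no gaps: "All AEs will be assigned a severity grade and relationship to study drug".

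**The concern.** The two missing-field rules in SAP 6.4 point in opposite directions. An event with no relationship stays in the table at its least favourable value. An event with no grade is removed. The SAP gives no reason for the difference.

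Removal acts on a count of subjects who reach a threshold, so it can only take subjects away. A footnote tells the reader that something was left out, but the tabulated count stays as it is. SAP 2.1 places safety in the primary objective, and results are shown by cohorts of about 12, where a single subject is visible.

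The wording is also loose. The table is unnamed, so a programmer could read the rule narrowly (the severity outputs only) or broadly (every adverse event summary). Under the broad reading, a subject whose only event is ungraded would also disappear from overall incidence.

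**Working it through.** The plan gives no figure to reproduce: no adverse event rate is stated, and the sample size rests on common practice.

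**Inputs.** N = 48 overall and 12 per cohort, both approximate (SAP 3.3 and 3.6). Let x be the number of subjects with a graded qualifying event. Let m be the number of subjects whose only possibly qualifying event has no grade. Let t be the number of those m who truly qualify, from 0 to m. The documents give neither x nor m, so the values below are assumptions: m from 1 to 3; x = 0, 1 or 3 in a cohort; x = 10 overall.

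**Counts.** The reported count is x and the true count is x + t. The error is x − (x + t) = −t, which is zero or negative. It is zero if every ungraded event is below the threshold. A subject who already qualifies in that row through another event is part of x and is not affected.

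**Largest effect per affected subject.** 1/48 = 2.1 points overall; 1/12 = 8.3 points in a cohort.

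**Percentages with a fixed denominator.** Reported: x/N. Highest possible truth: (x + m)/N.

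| N | x | Reported | Truth if all m qualify, m = 1 / 2 / 3 |
|---|---|---|---|
| 48 | 10 | 20.8% | 22.9% / 25.0% / 27.1% |
| 12 | 1 | 8.3% | 16.7% / 25.0% / 33.3% |
| 12 | 0 | 0% | 8.3% / 16.7% / 25.0% |

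**Percentages under the SAP 6.1 rule.** Reported: x/(N − m).

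- N = 48, x = 10, m = 1, ungraded event truly Grade 1: reported 10/47 = 21.3%, true 10/48 = 20.8%. The percentage is too high.
- N = 12, x = 3, m = 1, ungraded event truly Grade 1: reported 3/11 = 27.3%, true 3/12 = 25.0%. Again too high.
- N = 12, x = 0, m = 1, ungraded event truly Grade 2 or above: reported 0/11 = 0%, true 1/12 = 8.3%. The percentage is too low.

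**All combinations.** Taking every possible x and t for N = 12 and 48 and m = 1 to 3 gives 518 cases. With a fixed denominator, 0 are overstated, 344 understated and 174 unchanged. With the SAP 6.1 denominator, 250 are overstated, 250 understated and 18 unchanged. These are numbers of cases, not probabilities.

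**The case against.** The strongest reply is that the rule should rarely operate and hides nothing.

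- **Rarity.** The protocol requires a grade for every event. Protocol 14.3 and the SAP's Validation section already provide data checks and queries, and SAP 6.6 starts analysis only after the database is cleaned and locked. The rule is a fallback for what remains. This stands, and it is why the point is minor.
- **Disclosure.** Omitted events are footnoted and every event is listed, so with about 48 subjects a reader can bound the effect by hand. Serious events and those leading to discontinuation have their own tables, which do not depend on grade unless the rule is read broadly. This stands as mitigation, but the tabulated count is still not corrected.
- **Little depends on it.** The study is open-label and descriptive, with no comparator and no hypothesis tests, and the stopping criteria in Protocol 12.2 do not use these tables. One subject is also small beside sampling uncertainty: the exact 95% interval is 0 to 26.5% for 0 of 12, and 0.2 to 38.5% for 1 of 12. This stands too.
- **Imputing Grade 3 is a choice.** It is not the top of the scale, which runs to Grade 5 in Protocol Table 6, and it could place a mild event in the severe line. That is a real cost. Grade 3 is the level that Table 6 labels severe, and it is enough to qualify for both outputs.

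A reader might infer that severity rates can only be understated. The documents do not support that for percentages. It needs a fixed denominator, which SAP 7.10.1 does not state, and the general rule in SAP 6.1 could shrink the denominator. A reader might also infer that every affected subject lowers a rate by 2.1 or 8.3 points. Those are maxima, and the effect is often zero.

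**Conclusion.** The point holds for counts and is minor. As written, SAP 6.4 can make the number of subjects with a Grade 2+ or severe treatment-emergent event too low and can never make it too high. That is out of line with the cautious rules the same section applies to missing relationship and partial dates. The most that one affected subject can add is 2.1 points overall or 8.3 points in a cohort, at the planned sizes of 48 and 12.

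Two things rest on interpretation. The unnamed table is taken to mean the severity outputs, which is the natural reading but is not stated. Whether SAP 6.1 governs adverse event denominators is unclear; if it does, percentages can err in either direction. How many grades will be missing is unknown, and the mandatory grading suggests few.

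**What to change.** Replace the missing-severity sentence in SAP 6.4 with a rule that does four things:

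1. States that events with missing severity stay in all overall incidence tables of treatment-emergent events.
2. States that, after the pre-lock queries already planned, any event still ungraded is counted as severe (Grade 3) in the severe line of the overview and in the Grade 2+ table.
3. Sets the Safety population as the fixed denominator for these outputs, so that the general rule in SAP 6.1 does not apply to them.
4. Keeps the footnote and has it give the number imputed in each table, so that the figure without imputation can be recovered.

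The cost is a few lines of SAP text and a small programming change. No new data are needed and patient care is unaffected. The statistical price is that a truly mild ungraded event would be shown as severe, so the reported figures may be slightly less favourable. If the sponsor prefers not to impute, a missing-grade row with a worst-case count beside it would carry the same information.

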6.5 Interim Analysis

No interim analysis is planned.

6.6 Timing of Final Analyses

Data summary and statistical analysis will commence after all subjects have completed study Visit 7 (or discontinued prior to Visit 7) and the study database is cleaned and locked.

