### **6.1.2 Treatment Period**

During the Treatment Period, all eligible subjects will receive AK002 by IV infusion every 28 days. The first dose will be administered at the beginning of the treatment period Day 1 (Visit 2) after baseline measurements. At Day 141 ( $\pm 2$  days) (Visit 7), the final dose of AK002 will be given. Throughout the treatment period, subjects must maintain stable doses of their baseline AH dose and treatment regimen and remain on a stable treatment regimen through the end of the study. Patient's use of rescue medication will be monitored and reviewed throughout the treatment period and if necessary adjusted according to the current urticaria guidelines ([Zuberbier, 2014](#)). Subjects are expected to attend all site visits based on the assessment schedule (see [Table 3](#)).

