### **10.5.7.3 Anti-Drug-Antibodies**

Blood will be collected for determination of anti-drug antibodies (ADA) before the first dose at Day 1 (Visit 2), Day 29 (Visit 3), Day 85 (Visit 5), Day 155 (Visit 8), and Day 197 (Visit 10) at the study center. An unscheduled blood sample for ADA may be obtained if a related adverse event suspected of being associated with immunogenicity occurs.

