3.9.9 Prior, Concomitant, and Prohibited Medications

Prior medications and concomitant medications will be extracted from the Prior/Concomitant Medication CRF. Medications taken prior to Study Day 1 will be considered as prior medications and medications taken on or after Study Day 1 will be considered as concomitant medications. Prior and concomitant medications will be coded using WHO Drug Dictionary (WHODD March 2018 release) for Preferred Term (PT) and Anatomical Therapeutic Chemistry (ATC) classification.

Prohibited medications include, but are not limited to,

- Omalizumab
- H2-antihistamines
- Routine (daily or every other day during 5 or more consecutive days) doses of systemic corticosteroids
- Routine (daily or every other day during 5 or more consecutive days) doses of systemic hydroxychloroquine
- Routine (daily or every other day during 5 or more consecutive days) doses of methotrexate, cyclosporine A, cyclophosphamide, tacrolimus and mycophenolate mofetil
- Intravenous immunoglobulin G
- Plasmapheresis
- Regular (daily or every other day) doxepin (oral)
- Inactive vaccination
- Live attenuated vaccine
- Leukotriene Antagonists

4. Definitions

Table 4 Terminology and Definition

Terminology	Definition
Study Medication/Drug (SM)	AK002 administered by IV infusion.
Study Day	The first dose date (Day 1) is defined as the date on which a subject took the first dose of study medication (SM). Other study days are defined relative to Study Day 1. For visits prior to the first dose of the SM, Study Day is calculated as Visit Date – Day 1. For visits after the first dose, Study Day is calculated as Visit Date – Day 1 +1.
Enrolled	Subject who has signed informed consent, met all eligibility criteria at Screening, and having received the first dose of the study drug.
Completer for the Study	Subject who completes End of Study visit
Baseline	Baseline is defined as the non-missing value collected most recent to and before the time of the very first dose of the SM.
Prior Medication	Medication collected on the Prior/Concomitant Medication CRF, with start date prior to Study Day 1.
Concomitant Medication	Medication collected on the Prior/Concomitant Medication CRF, with end date on/after Study Day 1.
Treatment-emergent	Adverse events with onset date on or after the start of first study drug administration.

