7.2 Disposition of Subjects

Subjects (n and %) who completed or discontinued from the study will be tabulated by cohort and overall using all enrolled subjects. The primary reasons for study discontinuation will be included in the tabulation. The primary reasons may include any of the following:

- Subject withdrew consent
- Lost to follow-up
- Administrative reason
- Adverse event
- Investigator decision
- Failure to follow required study procedures
- Other

Subject disposition will be summarized for all Enrolled Subjects, MITT, Safety, and PP populations. A data listing will be presented for all enrolled subjects.

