7.7 Efficacy Analyses

7.7.1 Primary Efficacy Analysis

The primary efficacy variable is the change from baseline in UCT score for each population (CSU-XN, CSU-XF, UF, and CholU). UCT score and its change from baseline will be summarized using descriptive statistics by study visit (Weeks 4, 8, 10, 12, 16 for subjects enrolled under Protocol Amendment 2.1 and Weeks 4, 8, 12, 16, 20, 22, 24, and 28 for subjects enrolled after Protocol

Amendment 3). A 95% CI for the mean change will be computed. The summaries will be provided for each cohort.

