7.7.1.3 Secondary Efficacy Analyses

All summaries will be provided for each cohort.

- 1) Subjects achieving UCT CR and CMR will be tabulated with % of subjects for each visit. Subjects achieving a maximum of 0, 1, 2, 3, or 4 responses over the 8 post-baseline visits (subjects enrolled under Protocol Amendment 3) will also be tabulated. A 95% CI for the % responses will be calculated using the binomial distribution. Subjects achieving UCT DC will be similarly summarized.
- 2) Changes from baseline in UAS7 in CSU patients will be summarized similarly for each week the diary is collected. A 95% CI for the mean change will be reported. This analysis will also be carried out in the subgroup of CSU-XN patients with baseline UAS7 ≥ 16 .

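### SAP 6.6 permits the final analysis once Visit 7 (Week 20, last dose) is complete and the database locked, before the Week 22 primary visit; protocol endpoint 12 scores relapse at that same visit

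*SAP*

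**What the plan says.** **Timing of the analysis.** SAP 6.6 has two conditions. Analysis begins "after all subjects have completed study Visit 7 (or discontinued prior to Visit 7) and the study database is cleaned and locked". Protocol 6.1.2 shows what Visit 7 is: "Visit 7), the final dose of AK002 will be given". Protocol Table 1 and the schedules in both documents put it at Day 141, Week 20. Protocol 10.5.7.3 fixes two later visits: "Day 155 (Visit 8), and Day 197 (Visit 10) at the study center". The primary endpoint is the UCT change to Week 22 (Protocol 5.1; SAP 5.1), except for Amendment 2.1 subjects, for whom SAP 5.1 uses Week 10. SAP 5.1 fills a missing Week 22 value by LOCF and reports it beside the observed-data summary.

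**What the SAP intends to report.** SAP 7.7.1 summarises UCT at "Weeks 4, 8, 12, 16, 20, 22, 24, and 28 for subjects enrolled after Protocol" Amendment 3, and at "Weeks 4, 8, 10, 12, 16 for subjects enrolled under Protocol Amendment 2.1". SAP 7.7.1.3 counts responses per subject: "Subjects achieving a maximum of 0, 1, 2, 3, or 4 responses over the 8 post-baseline visits". SAP Section 4 defines a completer as "Subject who completes End of Study visit". SAP 7.2 adds: "Subjects (n and %) who completed or discontinued from the study will be tabulated by cohort and overall using all enrolled subjects".

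**Relapse.** Protocol endpoint 12 (Synopsis and 5.2) sets relapse, rebound and sustained effect at Visit 7. Objective 12 (Protocol 4.2) places relapse and sustained response in post-treatment follow-up, and Protocol 6.1.3 names relapse of symptoms among the reasons for having a follow-up period. SAP 3.7 declares no changes from the protocol's analyses.

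**The concern.** The visit named in SAP 6.6 is the last dosing visit, not the primary visit or the last study visit. The only other safeguard is the lock, and neither document says which visit the main-study lock waits for. Protocol Appendix 2 says that the database for the first six infusions may be locked before extended dosing ends, but names no last visit. Protocol 10.6 defines end of trial, not lock. SAP 6.6 also makes no provision for a subject who leaves between Visits 7 and 10.

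If the rule were applied at its minimum, subjects not yet at Visit 8 would have no Week 22 UCT. Their Week 22/LOCF value would be a Week 20 or earlier score, which reflects no full day after dose 6. They would also be neither completers nor discontinued in the disposition table.

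The endpoint 12 problem does not depend on the lock. Relapse after treatment cannot be observed on the day of the last dose, so the endpoint as written cannot serve its own objective.

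**Working it through.** **1. Reproduce the SAP's count of 8 visits.** Week = (day − 1)/7. Days 29, 57, 85, 113, 141, 155, 169 and 197 give Weeks 4, 8, 12, 16, 20, 22, 24 and 28. These are Visits 3 to 10, so 8 post-baseline visits, as in SAP 7.7.1.3.

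**2. What exists at Visit 7.** Visits 3 to 7 make 5. The remaining 8 − 5 = 3 (Weeks 22, 24 and 28) come later, and the primary visit is one of them.

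**3. Gaps and recall.** The UCT looks back 4 weeks (Protocol 10.4.2), taken as 28 days. Visit windows are ±2 days.

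| Visit | Day | Days after Visit 7 (range with windows) | UCT recall, days | Recall after dose 6 |
|---|---|---|---|---|
| 7 (Week 20) | 141 | 0 | 113–141 | 0 of 28 |
| 8 (Week 22) | 155 | 155 − 141 = 14 (153 − 143 = 10 to 157 − 139 = 18) | 127–155 | 14 of 28 |
| 9 (Week 24) | 169 | 28 (24 to 32) | 141–169 | 28 of 28 |
| 10 (Week 28) | 197 | 197 − 141 = 56 (195 − 143 = 52 to 199 − 139 = 60) | 169–197 | 28 of 28 |

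Visit 9 looks back over exactly one 28-day dosing interval after dose 6 and shares Days 141–155 (14 of 28) with Visit 8. At nominal days, Visit 10's recall starts 169 − 141 = 28 days after dose 6, so it lies wholly beyond that interval. With windows it starts 52 − 28 = 24 to 60 − 28 = 32 days after.

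**4. Where Visit 7 may come from.** The Amendment 2.1 schedule is not in the documents. SAP 3.1 calls Week 10 two weeks after the last dose for those subjects, which puts that dose at Week 8. Their listed UCT weeks 10, 12 and 16 are then 2, 4 and 8 weeks after it. Weeks 22, 24 and 28 are likewise 2, 4 and 8 weeks after Week 20. If Amendment 2.1 visits ran consecutively (screening, baseline, Weeks 4, 8, 10, 12, 16), Week 16 would be Visit 7 and the last listed. SAP 3.9.1, 3.9.6 and 5.6 also stop at Visit 7. A carry-over fits all of this but remains an inference.

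**5. Can extended dosing start before Visit 10?** Entry needs a Week 22 UCT of at least 12 and a later UCT of 5 or less (Protocol 6.1.4). The first scheduled visit after Week 22 is Day 169. Adding the 2 to 3 weeks of extension screening gives 169 + 14 = 183 to 169 + 21 = 190, before Day 197. A counting rule for these subjects is therefore needed.

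**6. Does an existing analysis capture loss of response?** SAP 7.7.1.3 gives response rates at each visit and a count of responses per subject. A subject responding only at Weeks 4, 8, 12 and 16 and one responding only at Weeks 20, 22, 24 and 28 both score 4. The count does not show whether response was kept after the last dose.

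**The case against.** The strongest reply is that nobody plans an analysis at Week 20. SAP 6.6 also requires a cleaned and locked database. Protocol 6.1 says the objectives are evaluated at Weeks 22, 24 and 28, SAP 3.2.2 gives the main study an 8-week follow-up, SAP 7.7.1 summarises through Week 28, and SAP 6.5 plans no interim analysis. The observed-data Week 22 summary would show any shortfall in n, and no hypothesis is tested. All of this stands. A reader might infer that the plan will analyse before its primary endpoint; the documents do not support that.

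A reader might also infer that SAP 6.6 contradicts the Week 28 summaries, the eight-visit count, the completer definition and the disposition table. It does not: a lock after Week 28 satisfies all of them together. The rule is too permissive, not contradictory.

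On relapse, the SAP takes precedence over the protocol's analyses (Protocol 13; SAP Introduction), and no readable SAP text scores relapse at Visit 7. A reader might infer that the follow-up UCTs go unused; they are summarised by visit, counted per subject and listed. SAP 5.3 and 7.7.2 are partly redacted, so only the readable text can be judged. The extended-dosing entry rule does describe recurrence per subject, but it serves eligibility, also requires a Day 1 UCT of 5 or less and excludes one cohort. What survives is that the endpoint's time point is wrong as written and the readable SAP has no table of response kept or lost after the last dose.

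**Conclusion.** The point holds in two parts, and both should be corrected.

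- **SAP 6.6** names a visit 14 days (10 to 18) before the primary visit and 56 days (52 to 60) before End of Study, with 3 of 8 post-baseline UCT visits outstanding. It permits an early analysis with LOCF in place of late Week 22 values. Such an analysis is unlikely, and the number of subjects it would affect cannot be derived from the documents. The Week 22 part concerns subjects outside Amendment 2.1.
- **Protocol endpoint 12** is set at a visit with zero days of post-treatment follow-up, against objective 12 and section 6.1.3. This is certain from the text and independent of lock timing.

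The recall figures assume visits on their nominal days, except where ranges are given. The origin of Visit 7 in the Amendment 2.1 schedule is an inference and the verdict does not rest on it.

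**What to change.** 1. **SAP 6.6.** Tie database lock and final analysis to every subject having completed Visit 10/Week 28 (or the last visit of the Amendment 2.1 schedule), discontinued earlier, or entered extended dosing before Visit 10.
2. **Protocol endpoint 12 (Synopsis and 5.2).** Move it to the post-treatment follow-up visits, with Visit 10/Week 28 as the main time point and Visit 9 as supportive, for the recall reason shown in the working.
3. **SAP tabulation.** By cohort, give n, % and 95% CI of Week 22 UCT responders who keep or lose response. Use the SAP Section 4 definitions, which take precedence over the protocol's UCT = 16 for complete response, and name the category used. Define relapse and rebound before lock. State how subjects entering extended dosing before Visit 10 are counted. State also how Amendment 2.1 subjects are mapped: by weeks since last dose, their Weeks 10, 12 and 16 correspond to Weeks 22, 24 and 28, which the sponsor should confirm against that schedule.
4. **Consistency corrections only.** In SAP 3.1, four weeks after Week 22 is Week 26, not the stated Week 24, and the SAP's own schedule ends at Week 28. Align the visit ranges in SAP 3.9.1, 3.9.6 and 5.6 with the schedule table.

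The cost is wording in both documents and one small descriptive table from UCTs already scheduled. With about 12 subjects per cohort its intervals will be wide. The downside is a wait of up to about 8 weeks (56 days) after the last subject's Visit 7.
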